16.6 Missing Data

Missing data are expected to be low in this prospective study, however, every attempt will be made to follow-up with patients to complete questionnaires. Patients will not be replaced if the data of primary endpoint are missing, instead, we will record and summarize the pattern of missing data. Exploratory analysis using simple imputation and/or multiple imputation maybe performed as appropriate. We plan to use last values carried forward for the initial 14 day daily data.

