 5. Beginning on Day 1 of active treatment and continuing for 14 consecutive days, complete Appendix V daily pre/post therapy. If no therapy is received on a day during this timeframe, complete once daily. To be filled out only for primarily treated area. For post-therapy questionnaires VIA and VIB.
 6. Prior to the last therapy.
 7. Appendix IX A or B, as labeled depending on pain or neuropathy area to be treated.
 8. If patient provides written consent for AV recording. Recording may be done on any day.
 9. Appendix XII A or B, as labeled depending on pain or neuropathy area to be treated.
 10. To be completed any time after completion of active treatment.
 11. Optional use in selected patients: Blood draws are completed at Baseline (prior to treatment) and on the last planned day or two of treatment (e.g., Day 9 or 10, if 10 treatments are given but sooner if earlier treatment completion is planned) (±2 days). Ideally, do prior to treatment. See [Section 14.0](#).
 12. fMRI: Optional use in selected patients, do at baseline and on approximately the last day of the initial treatment (±1 day).
 13. Quantitative sensory testing: Optional use in selected patients, do at baseline and then the last day of the initial treatment (±3 days) on 10 patients from each cohort. Do prior to treatment.
 14. For TENS patients only: Study Coordinator or Nurse to call on Treatment Day 2 and once on Treatment Day 8-10 to assess toxicities and remind the patient to complete daily questionnaires and mail them back.
- R Research funded

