8.0 Dosage Modification Based on Adverse Events

If a patient develops any substantial toxicity from the treatment (not expected), then treatment with either TENS or Scrambler therapy should be stopped.

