14.4 Background and Methodology

14.41 mRNA Gene Expression

We, through [name] lab, will obtain RNA expression levels that will be directly comparable to the originally reported assay, i.e., relative changes such as before and after treatment. This result will be expressed as a "fold change", such as saying "after scrambler the expression levels of gene X was increased 2-fold and Y was diminished to 0.7-fold." That calculation will be made relative to a reference gene that is assumed to be stable.

We will do RNA quantification genome-wide. The panel will then represented by genes of interest and a dozen reference genes, out of ca. 11,000-15,000 genes for which reliable expression levels will be available.

Via this process, we will look at all of the interesting-appearing genes from the Starkweather et al manuscript. This method will allow us to, hopefully, confirm that the gene changes were in line with that previously reported.

15.0 Drug Information – Not applicable**16.0 Statistical Considerations and Methodology****16.1 Primary Endpoint**

The primary endpoint of this study is the proportion of patients who achieve at least 50% reduction in pain or tingling scores from baseline after two weeks of therapy.

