16.3 Analysis Plan**16.31 Primary endpoint**

Evaluate the efficacy of Scrambler therapy compared to TENS therapy for pain and/or tingling related to CIPN.

The main efficacy endpoint is defined as achieving 50% reduction in pain or tingling from baseline. At enrollment, patients will be asked to select either pain or tingling as their primary symptom of concern. Allowing the patients to select their main symptom (pain or tingling) is reasonable since the scores and the patterns of reduction were similar for pain and tingling after Scrambler therapy as shown by Pachman et al. (Pachman, Weisbrod et al. 2014)

Descriptive statistics (mean, sd, median, range) of pain and tingling scores and changes pre- and post-treatment scores will be summarized and the percentage of pain and tingling reduction from baseline will be calculated for each timepoint, separately by treatment arm. Longitudinal plots of scores by arm will be provided. The frequency and percentages of patients who achieved more than 50% reduction in pain and/or tingling scores after 2 weeks of therapy (scores from the last treatment day compared to the pre-treatment data, using the question related to average symptom [pain or tingling, whichever the patient chose when entering the study] over the previous 24 hours) and after 8 weeks of observation (scores from Week 8 form) from baseline (scores from Day 1 pre-treatment form) will be summarized by treatment arm and will be compared between arms using a Chi-square test (or Fisher-exact test as appropriate).

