16.5 Sample size

The sample size of 50 patients (25 per arm) in this prospective randomized study is mostly determined by feasibility. This study is not designed as a confirmatory study, hence, not powered as such. The primary purpose of this study is to estimate the effect of scrambler therapy for the treatment of CIPN which will inform hypothesis formulation for future studies. If the data from this study suggest a clinically non-ignorable effect of scrambler therapy compared to TENS therapy, we will plan for a larger study to confirm its benefit. However, if the data from this trial show a very large difference in changed pain scores between the two arms, such that the primary endpoint is positive with a p-value of less than 0.05, we will interpret this outcome as evidence that Scrambler therapy is better than TENS therapy, or vice-versa, depending on which arm is doing better.

More than 45% of patients in Pachman et al.'s study experienced treatment effect (50% or more reduction in symptom scores) after 2 weeks of scrambler therapy (Pachman, Weisbrod et al. 2014). This estimate includes patients who were enrolled early in the trial who did not respond to the treatment as well as the later cohort, potentially due to the study team's inexperience in the beginning of the trial. With the current level of experience, we expect a much higher percentage of reduction in patients' symptom scores after scrambler therapy in this trial. The likelihood of detecting an improvement of 30% or more after scrambler therapy compared to TENS is high with a sample size of 25

patients per arm. Table 16.51 shows the minimum detectable improvement with at least 80% power at a one-sided .05 significance level for various plausible scenarios with 25 patients per arm.

Table 16.51. Minimum Detectable Improvement with 80% power at a one-sided 0.05 significance level

Proportion of patients achieving 50% or more reduction in symptom scores from baseline		Minimum Detectable improvement	Power (%)
TENS	Scramber		
.05	.32	.27	80
.10	.40	.30	80
.20	.54	.34	81
.30	.65	.35	81
.40	.75	.35	82

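### Carrying the last value forward, and scoring on the last treatment day, can count an early reduction as a two-week response; with 25 per arm, one to three such patients can cross p<0.05

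*Combined protocol and SAP*

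**What the plan says.** Section 16.1 makes the primary endpoint "the proportion of patients who achieve at least 50% reduction in pain or tingling scores from baseline after two weeks of therapy". Section 16.31 says which scores are used: "scores from the last treatment day compared to the pre-treatment data, using the question related to average symptom", for the symptom (pain or tingling) that the patient chose at entry. The arms are then "compared between arms using a Chi-square test (or Fisher-exact test as appropriate").

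The Section 4.0 test schedule has the pre-treatment questionnaire (Appendix V) completed on 14 consecutive days from Day 1. Footnote 5 adds: "If no therapy is received on a day during this timeframe, complete once daily".

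On missing data, 16.6 expects little of it, does not replace patients, and will record and summarise the pattern. Simple or multiple imputation is exploratory and optional. The one rule stated as a plan is: "We plan to use last values carried forward for the initial 14 day daily data".

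Section 16.5 calls the trial non-confirmatory, but adds a condition and its reading: "the primary endpoint is positive with a p-value of less than 0.05, we will interpret this outcome as evidence that Scrambler therapy is better". The comparator there is TENS, and the rule is reversed if TENS does better.

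**The concern.** The endpoint is meant to describe the patient's state at the end of two weeks. Two parts of the plan allow an earlier score to stand in for it.

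- **Lost forms.** The endpoint score is one of the 14-day daily scores. On a plain reading, the carry-forward rule fills it when later forms are missing. A patient whose last returned form shows a halved score is then a responder, whatever happened afterwards. Section 16.6 does not say outright whether the rule fills the primary endpoint.
- **Early stopping.** Under 16.31 a patient who stops on day 3 has an observed last-treatment-day score. That score counts with no imputation at all, although 16.1 speaks of two weeks.

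The timing also differs by arm. TENS is used for 14 days. Scrambler is given on up to 10 weekdays, only while a symptom is rated above 0, so its last treatment day can come well before day 14.

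At stake is the 16.5 reading of p<0.05 as evidence that one therapy is better. In a trial of 50 patients, a few classifications can settle it.

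**Working it through.** **1. The plan's own figure.** Table 16.51 (25 per arm, one-sided 0.05) reproduces with the pooled-variance formula

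power = Φ{[(p2 − p1)√n − 1.645√(2p̄(1 − p̄))] / √[p1(1 − p1) + p2(1 − p2)]}.

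First row: p1=0.05, p2=0.32, p̄=0.185, so (1.350 − 0.903)/0.515 = 0.867 and power is 80.7%. The other rows give 80.4, 81.7, 81.3 and 82.1%, against 80, 81, 81 and 82% stated. The table is not in question here. It assumes that all 25 patients per arm yield a score.

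**2. How few patients change the reading.** With 25 per arm, a Scrambler and c TENS responders, and R = a + c, the Pearson statistic reduces to

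X² = 50(a − c)² / [R(50 − R)], 1 df, two-sided.

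| Scrambler | TENS | X² | p |
|---|---|---|---|
| 9 | 5 | 800/504 = 1.59 | 0.208 |
| 10 | 5 | 1250/525 = 2.38 | 0.123 |
| 11 | 5 | 1800/544 = 3.31 | 0.069 |
| 12 | 5 | 2450/561 = 4.37 | 0.037 |

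Three reclassified patients take a clearly null table across 0.05; at the boundary one does. The same happens at other TENS counts: 8 vs 3 gives 0.088 and 9 vs 3 gives 0.047; 14 vs 8 gives 0.087 and 15 vs 8 gives 0.047. Under Fisher's test the crossing moves by one patient: 12 vs 5 gives 0.072 and 13 vs 5 gives 0.038.

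**3. The same data under three rules.** Suppose TENS has 5/25, and Scrambler has 10 observed responders plus 2 patients whose forms end early on a halved score.

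- LOCF: 12/25 vs 5/25, p=0.037.
- Missing counted as non-response: 10/25 vs 5/25, p=0.123.
- Complete cases: 10/23 vs 5/25, X² = 48 × 135² / (23 × 25 × 15 × 33) = 3.07, p=0.080.

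**4. Chance of a false reading under an assumed pattern.** Let everyone else in both arms respond at one common rate. Let k patients in one arm, not true two-week responders, be carried forward as responders. Summing exact binomial probabilities over tables with p<0.05 in favour of that arm gives:

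| Common rate | k=0 | 1 | 2 | 3 | 4 |
|---|---|---|---|---|---|
| 10% | 2.4% | 5.1% | 9.5% | 16.1% | 25.1% |
| 20% | 2.7% | 4.5% | 7.1% | 10.8% | 15.8% |
| 30% | 2.7% | 4.0% | 5.9% | 8.6% | 12.1% |
| 40% | 3.0% | 4.2% | 5.9% | 8.1% | 10.8% |

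If those k patients count as non-responders, the figure is at most 2.3% for k=1 to 4. The test is symmetric, so the table applies to either arm. The values of k and the common rates are assumptions; the documents give no missing-data rate.

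**5. The assessment day.** Under Section 7.121 a Monday start without breaks puts ten sessions on days 1–5 and 8–12, so the last is on day 12. A Wednesday start ends on day 14 (days 1–3, 6–10 and 13–14). Scheduling may extend to 16 calendar days. TENS ends on day 14. The last treatment day is therefore not one time point across arms, even with full compliance.

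**The case against.** **Stopping treatment is not missing data.** Footnote 5 keeps the daily form going on days without therapy. A patient who stops should still supply scores, so LOCF acts only when forms are not returned. This stands. It makes the assessment day in 16.31 as important as the imputation rule, since changing 16.6 alone would leave the early stopper scored as now.

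**Direction.** A reader might infer that LOCF favours Scrambler, because its effect is described as rapid and only that arm attends daily. The documents do not support this. Clinic attendance should help form capture, whereas TENS patients treat themselves and mail forms back after reminder calls, so losses in TENS are at least as plausible. LOCF also carries early non-response forward, and it carries the last value rather than the best: a patient who relapses while still completing forms carries the relapsed score. If three patients are carried forward as responders in each arm, 9 vs 5 becomes 12 vs 8, p=0.25, and nothing flips.

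**Toxicity.** A reader might take the Section 8.0 rule that "treatment with either TENS or Scrambler therapy should be stopped" to mean that early stoppers are likely. The same sentence says that substantial toxicity is not expected.

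**Non-response is not neutral either.** If the truth is 12 vs 8 (p=0.25) and three TENS responders' forms are lost, counting them as failures gives 12 vs 5, p=0.037. This stands, and it is why sensitivity analyses must be committed in advance.

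**Already handled, and not confirmatory.** Section 16.6 will summarise the missing-data pattern, so missingness would not be hidden. It commits to no alternative analysis, however, and the p<0.05 reading in 16.5 remains despite the exploratory label.

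**Conclusion.** The concern holds in limited form. As written, a score from before the end of two weeks can decide the primary endpoint by two routes: the last-treatment-day definition in 16.31 and the carry-forward rule in 16.6. With 25 per arm, one to three reclassified patients can move the comparison across the threshold that 16.5 treats as evidence.

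Its size in this trial is unknown. If missing forms and early stopping are as rare as the plan expects, the effect may be nil; if they are balanced between arms, it largely cancels. A systematic bias towards Scrambler is not established. The conclusion rests on the plain reading that LOCF fills the endpoint score, on the assumed counts above, and on the chi-square test; Fisher's test moves the crossing by one patient without removing it.

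**What to change.** 1. Reconcile 16.1 and 16.31 on one end-of-two-weeks assessment day for both arms. The daily form already due on day 14, whether or not therapy was given, can supply the score. Early stoppers, including Scrambler patients whose symptoms reached 0, are then scored on observed data. Say what applies when a Scrambler course runs past day 14.
2. In 16.6, keep every randomised patient in the denominator of the assigned arm, and count a score still missing at that day as non-response in the primary analysis.
3. Commit to LOCF and multiple imputation as sensitivity analyses, and report the number and timing of missing scores by arm.

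These should be settled before anyone sees which patients have missing scores. The cost is a few sentences and no new data collection. Responder rates may be slightly lower in both arms, and TENS may be penalised if more of its mailed forms are lost; the sensitivity analyses and the counts by arm would show that.

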16.7 Data and Safety Monitoring

The study chair(s) and the study statistician will review the study at least twice a year to identify accrual, adverse event, and any endpoint problems that might be developing. The Mayo Clinic Cancer Center (MCCC) Data Safety Monitoring Board (DSMB) is responsible for reviewing accrual and safety data for this trial at least twice a year, based on reports provided by the MCCC Statistical Office.

16.8 Adverse Event Stopping Rules

16.81 The stopping rules specified below are based on the knowledge available at study development. We note that the Adverse Event Stopping Rule may be adjusted in the event of either (1) the study re-opening to accrual or (2) at any time during the conduct of the trial and in consideration of newly acquired information regarding the adverse event profile of the treatment(s) under investigation. The study team may choose to suspend accrual because of unexpected adverse event profiles that have not crossed the specified rule below.

16.82 Adverse events will be monitored separately by arm. Accrual will be temporarily suspended to this study if at any time we observe events considered at least possibly related to study treatment (i.e. an adverse event with attribute specified as “possible”, “probable”, or “definite”) that satisfy either of the following:

- if 3 or more patients in the first 10 treated patients experience a grade 3 or higher adverse event.
- if after the first 10 patients have been treated, 30 % of all patients experience a grade 3 or higher adverse event.

- if any grade 5 adverse events are observed that are related to study treatment.
- 16.83 If accrual is temporarily suspended, the study will be reviewed to determine whether accrual should continue or be permanently closed.
- 16.84 We note that we will review Grade 4 and 5 adverse events deemed “unrelated” or “unlikely to be related”, to verify their attribution and to monitor the emergence of a previously unrecognized treatment-related adverse event.

16.9 Gender and minority accrual considerations

This study is open to patients from all races. Historical data indicate that no more than 10% of patients will be ethnic minorities. Subset analysis along ethnic subpopulations will hence have a lack of power to draw substantive conclusions but will provide some data for future meta-analytic procedures and hypotheses generation.

Ethnic Category	Sex/Gender (%)			
	Females	Males	Unknown	Total
Hispanic or Latino	0	1	0	1
Not Hispanic or Latino	30	19	0	49
Ethnic Category: Total of all subjects	30	20	0	50
Racial Category				
American Indian or Alaskan Native	1	0	0	1
Asian	1	1	0	2
Black or African American	1	2	0	3
Native Hawaiian or other Pacific Islander	0	1	0	1
White	27	16	0	43
Racial Category: Total of all subjects*	30	20	0	50

Ethnic Categories: **Hispanic or Latino** – a person of Cuban, Mexican, Puerto Rican, South or Central American, or other Spanish culture or origin, regardless of race. The term “Spanish origin” can also be used in addition to “Hispanic or Latino.”
Not Hispanic or Latino

Racial Categories: **American Indian or Alaskan Native** – a person having origins in any of the original peoples of North, Central, or South America, and who maintains tribal affiliations or community attachment.

Asian – a person having origins in any of the original peoples of the Far East, Southeast Asia, or the Indian subcontinent including, for example, Cambodia, China, India, Japan, Korea, Malaysia, Pakistan, the Philippine Islands, Thailand, and Vietnam. (Note: Individuals from the Philippine Islands have been recorded as Pacific Islanders in previous data collection strategies.)

Black or African American – a person having origins in any of the black racial groups of Africa. Terms such as “Haitian” or “Negro” can be used in addition to “Black or African American.”

Native Hawaiian or other Pacific Islander – a person having origins in any of the original peoples of Hawaii, Guam, Samoa, or other Pacific Islands.

White – a person having origins in any of the original peoples of Europe, the Middle East, or North Africa.

17.0 Pathology Considerations/Tissue Biospecimens - Not applicable

18.0 Records and Data Collection Procedures

18.1 Submission Timetables

18.11 Initial Material(s)

	Active-Monitoring Phase (Compliance with Test Schedule Section 4.0)
Case Report Form (CRF)	
On-Study	≤2 weeks after registration
Research Submission (see Sections 4.0 and 14.0)	
End of (ALL) Active Treatment/Cancel Notification	Submit ≤2 weeks after registration if withdrawal/refusal occurs prior to beginning protocol therapy
Patient Questionnaire	≤2 weeks after registration - Patient questionnaire booklet must be used; copies are not acceptable for this submission
Booklet Compliance	≤2 weeks after registration - This form must be completed only if the booklet(s) contains absolutely NO patient provided assessment information

18.12 Test Schedule Material(s)

	Active-Monitoring Phase (Compliance with Test Schedule Section 4.0)		
	At each evaluation during treatment	Observation	At end of treatment
CRF			
Adverse Event	X	X	
Research Submission (see Sections 4.0 and 14.0)	X	X	
End of Initial Treatment			X
Optional Crossover Continuation		X	
Patient Questionnaire ¹	X	X	X
Booklet Compliance ²	X	X	X
End of (ALL) Active Treatment/Cancel Notification			X
ADR/AER (see Section 10.0)	At each occurrence		

1. Patient questionnaire booklet **must** be used; copies are not acceptable for this submission.
2. This form must be completed **only** if the booklet contains absolutely **NO** patient provided assessment information.

19.0 Budget

19.1 Costs charged to patient: routine clinical care.

19.2 Scrambler therapy and TENS units will be provided *gratis*.

19.3 Additional tests will be provided *gratis* including: fMRI, Quantitative Sensory Testing, and mRNA gene expression labs. Audiovisual recording will not be charged to the patient.

19.31 mRNA budget details

19.311 Blood draw and processing charges including CBC with differential:
Included as part of CRTU.

19.312 Processing charges

[Redacted]

19.313 Analysis charges:

[Redacted]

19.32 fMRI associated budget detail

Budget: Harvard Team

[Redacted]

19.33 Quantitative Sensory Testing Budget

[Redacted]

Appendix I Patient instruction sheet for tapering gabapentin and pregabalin

Tapering of gabapentin or pregabalin will preferably occur over two weeks. Lower doses may be tapered over one week to accommodate patient availability with approval of [name]. During first week of taper, drug will be reduced approximately 25% for 3-4 days, then an additional 25% so that the drug has been reduced by approximately 50% by the end of the first taper week. Drug will continue to be reduced during the second week every few days until the final dose is taken the evening prior to treatment. Patient provider or [name] will need to be contacted if different doses of pills are needed. Patients will be instructed on potential symptoms of withdrawal and be asked to contact study staff if symptoms are experienced, as the taper may need to be adjusted. The decision of which dose to begin tapering (morning, noon, evening) will be decided between patient and study staff.

Patient Form

Gabapentin/Pregabalin (circle one)	mg	mg	mg	mg
Day/Date				
1= / /	pills	pills	pills	pills
2= / /	pills	pills	pills	pills
3= / /	pills	pills	pills	pills
4= / /	pills	pills	pills	pills
5= / /	pills	pills	pills	pills
6= / /	pills	pills	pills	pills
7= / /	pills	pills	pills	pills
8= / /	pills	pills	pills	pills
9= / /	pills	pills	pills	pills
10= / /	pills	pills	pills	pills
11= / /	pills	pills	pills	pills
12= / /	pills	pills	pills	pills
13= / /	pills	pills	pills	pills
14= / /	pills	pills	pills	pills
Day 1 of Treatment	0 pills	0 pills	0 pills	0 pills

Potential symptoms of gabapentin withdrawal may include nausea, insomnia, restlessness, agitation, anxiety, disorientation, confusion, light sensitivity, sweating, headaches, palpitations, chest pain, and flu-like symptoms.

**Appendix IIA Peripheral Neuropathy Questionnaire for Upper Extremity Neuropathy
(Used for Eligibility)**

Initials _____
Study # _____
Date _____
Day _____

How much of a problem has **pain** in your fingers or hands been **in the past week**?

0	1	2	3	4	5	6	7	8	9	10
No pain in fingers and/or hands										Pain in fingers and/or hands as bad as you can imagine

How much of a problem has **tingling** in your fingers or hands been **in the past week**?

0	1	2	3	4	5	6	7	8	9	10
No tingling in fingers and/or hands										Tingling in fingers and/or hands as bad as you can imagine

**Appendix IIB Peripheral Neuropathy Questionnaire for Lower Extremity Neuropathy
(Used for Eligibility)**

Initials _____
Study # _____
Date _____
Day _____

How much of a problem has **pain** in your toes or feet been **in the past week**?

0	1	2	3	4	5	6	7	8	9	10
No pain in toes and/or feet										Pain in toes and/or feet as bad as you can imagine

How much of a problem has **tingling** in your toes or feet been **in the past week**?

0	1	2	3	4	5	6	7	8	9	10
No tingling in toes and/or feet										Tingling in toes and/or feet as bad as you can imagine

